5.3 Data Derivations

Baseline and Change from Baseline

Baseline and change from baseline will be calculated for all assessments, including additional assessments (if applicable), as follows:

- Baseline value is defined as the last available value prior VTX-801 dosing, if not defined otherwise in the study protocol. Assessments that occurred on the same day as VTX-801 dosing, when time of assessment is not available, will be assumed to be prior to VTX-801 dosing (unless the assessment is planned after VTX-801 dosing in the study protocol).
- Change from baseline will be calculated for any post-baseline data as the difference between the post-baseline assessment value and the baseline value.

Study Day

Study day will be calculated as (assessment/sample date – date of first study treatment dose) for pre-baseline assessments and [(assessment/sample date – date of first study treatment dose) + 1] for post-baseline assessments, i.e., there will be no study day 0 and study day 1 will correspond to the first study treatment dose.

5.4 Other Data Analyses Considerations

Centre Effect Management

Not Applicable.

Subgroup Analyses

Not Applicable.

Other Strata and Covariates

Not Applicable.

Multiple Comparisons and Multiplicity

Not Applicable.

6 Analysis Sets

Analysis sets to be used for the analyses are described in the table below.

Table 2: Analysis Sets

Analysis Set	Description
Screened set	The Screened set will include all patients who were enrolled (signed informed consent) regardless of whether they received the study drug or not.
Safety set	The Safety set will include all patients who received at least part of the VTX-801 dose. This analysis set will be used for all safety analyses.
Pharmacodynamics set	The Pharmacodynamics set will include all patients who received at least part of the VTX-801 dose and who have at least one post-baseline pharmacodynamics assessment (free serum Cu (CuEXC and ANCC), REC, RAC, total serum Cu, 24-hour urinary Cu and serum ceruloplasmin by enzymatic activity assay and by nephelometry).
Efficacy set	The efficacy set will include all patients who received at least part of the VTX-801 dose and who have at least one post-baseline radiocopper assessment.

Given that the study was early terminated and an abbreviated CSR focusing mostly on safety data will be prepared, Pharmacodynamics Set and Efficacy Set will not be used in any analysis.

7 Methods of Analysis

7.1 General Considerations

N

N will be the number of patients in the specified population and cohort.

Continuous data

Continuous data will be summarized using: the number of patients with non-missing observations (n), mean, median, standard deviation (SD), minimum and maximum.

Continuous variables will be reported with the same number of decimal places as collected in the CRF except for mean and median (+1 decimal place) and standard deviation (+2 decimal places).

Categorical data

Categorical data will be summarized using: the number of patients with non-missing observations (n), count/number of events (if applicable) and percentage of each category.

- All categories will be presented, even if no patients are counted in a particular category, unless otherwise stated.
- In case 1 or more patients have missing data for the summary, the number with missing data will be presented as a separate category, labelled accordingly as 'Missing', if not otherwise stated.
- Counts of zero in any category will be presented without percentage.
- All summary percentages will be calculated using N as the denominator, unless otherwise stated.
- For AEs, medical history, prior and concomitant medications, the counts are based on single counts of patients with multiple events/treatments under the same category, while the percentages are calculated using N. Counts will be displayed by descending order of frequency for the overall group, unless otherwise stated.

Data presentation

- Outputs: generated directly in rtf format using ODS RTF within SAS. Outputs will be delivered in a single combined pdf file.
- Page Orientation: Landscape.
- Font: Courier New font with minimum of 9-point font size.
- Margins: top: 3cm, bottom: 2cm, left: 3.8cm and right: 2cm on A4 paper.
- Column headers will be left aligned.
- Page headers will include the name of the sponsor, and the date of database lock and data extraction.

7.2 Patient Disposition

Patient disposition data will be presented by dose cohort and overall.

The number and percentage of patients belonging to the following categories will be presented along with the reason for discontinuation: enrolled, screened, screening discontinuation, completed the study, discontinuation from the study.

The number and percentage of patients in each analysis set will also be presented.

In addition, information on analysis sets, study completion and discontinuation will be listed.

7.3 Protocol Deviations

The list of potential protocol deviations, including classification (Important/Non-important) for each protocol deviation, will be pre-defined in the Protocol Deviation Criteria Form (PDCF).

Prior to data lock for analysis, a meeting will be held to review protocol deviation classification, and to agree on the analysis sets.

The number and percentage of patients with at least one important deviation will be provided separately for each cohort and overall.

Important protocol deviations will also be summarized (frequencies and percentages) by deviation category and overall, on the Safety Set.

A listing of all important protocol deviations will be provided for all patients.

7.4 Demographics and Baseline Characteristics

The following demographic and baseline characteristics will be summarized using descriptive statistics and presented by dose cohort and overall using the SAF:

- Age at baseline (years) – continuous and categorical (18-64, 65-84, >=85),
- Gender,
- Childbearing / Reproductive potential,
- Race,
- Ethnicity,
- Smoking history, and alcohol consumption
- Height at baseline (cm),
- Weight at baseline (kg),

- BMI (kg/m²).

The following disease characteristics will be summarized using descriptive statistics and presented by dose cohort and overall using the SAF:

- Time since Wilson Disease diagnosis,
- Leipzig score at diagnosis,
- ATP7B genotyping performed by CLIA certified laboratory,
- Gene/codon/amino acid change as reported in the eCRF.

All the above will also be provided in listings for all patients.

7.5 Medical History

Medical history and concomitant diseases will be coded using MedDRA dictionary.

Medical histories are defined as events reported on the General Medical History eCRF pages, which ended before the first study treatment date.

Concomitant diseases are defined as diseases which started before the first study treatment date but were ongoing at the first study treatment date, or disease which started on or after VTX-801 dosing.

The number and percentage of patients with a medical history will be tabulated by dose cohort and overall, by System Organ Class (SOC) and Preferred Term (PT), using the SAF. A by-patient listing will be produced.

The number and percentage of patients with a concomitant disease will be tabulated by dose cohort and overall, for each SOC and PT, using the FAS. A by-patient listing will be produced.

7.6 Prior and Concomitant Medications

Prior and concomitant medications will be coded using WHOHD dictionary.

Medications will be defined as follows:

- Prior Medication: any medications with start date before VTX-801 dosing.
- Concomitant Medication: any medications with end date either the same or after VTX-801 dosing or missing.

Any medications with start date before the first study treatment date and end date either after the first study treatment date or missing will be assumed to be both prior and concomitant medication.

The number and percentage of patients with prior and concomitant medications will be tabulated by cohort and overall, by Anatomical Therapeutic Chemical Classification (ATC) and preferred term (PT) on the SAF. A by-patient listing will be produced for prior and concomitant medications as well as for all prior therapies.

Prior and concomitant medications attached to WD will be listed.

Surgery and Medical Procedures:

Surgery and Medical Procedures will be listed on the SAF.

7.7 Treatment Exposure and Compliance

VTX-801 administration and infusion parameters will be reported using listings.

7.8 Efficacy and Pharmacodynamic (PD) Analyses

Unless otherwise specified, the following endpoints will be listed.

Secondary endpoints:

- Free serum Cu [may include measurement by assay for CuEXC and/or ANCC],
- REC, RAC, total serum Cu and 24-hour urinary Cu,
- Serum ceruloplasmin activity (enzymatic assay),
- VTX-801 responder status [REDACTED]
- VTX-801 Responder status,
- Humoral and cellular immune response to VTX-801:
 - In vitro neutralizing antibodies (Nab) anti-AAV3B capsid assay,
 - ELISA: antibodies against AAV3B capsid and miniATP7B transgene,
 - IFN-gamma ELISpot to AAV3B capsid and miniATP7B transgene

Exploratory endpoints:

- Hepatic Cu and histology from liver biopsy,
- Ceruloplasmin level determination by nephelometry,
- Unified Wilson's Disease Rating Scale,
- Liver Magnetic Resonance elastography,

- Hepatic synthetic function (INR, platelet count, albumin),
- Model for End-Stage Liver Disease, AST to platelet ratio index, Fibrosis-4 Index for Liver Fibrosis,
- Mini International Neuro-psychiatric Interview,
- Symbol Digit Modality Test and Stroop test,

7.9 Safety Analyses

All safety analyses will be performed using descriptive statistics by cohort and overall using the SAF, unless otherwise specified.

7.9.1 Adverse Events

Adverse events (AEs) will be coded using MedDRA dictionary.

AEs will be graded according to the National Cancer Institute – Common Terminology Criteria for Adverse Events (NCI-CTCAE) version 5, based on study protocol.

The following definitions will be used:

- Treatment-emergent AEs (TEAEs): AEs that occurred during on-treatment period, from the day of VTX-801 dosing,
- Related AEs: AEs suspected by the Investigator to have a relationship to study treatment (as recorded on the AE eCRF page, Relationship to VTX-801 = Possibly related, Probably related, Definitely related or missing,
- Serious Adverse Events (SAE): serious AEs (as recorded on the AE eCRF page, Does AE Meet the Definition of an SAE = Yes),
- AEs leading to Death: adverse event leading to death (as recorded on the AE eCRF page, Results in death, or Outcome = Fatal, or Grade = 5),
- Liver function AEs: adverse event meeting the definition of a suspected DILI (as recorded on the AE eCRF page, does AE meet the definition of a suspected DILI event? = Yes).

An overview summary table will present the number and percentage of patients with a TEAE, including:

- TEAEs / TEAEs related to study treatment,
- Serious TEAEs / Serious TEAEs related to study treatment,
- Liver TEAEs / Liver TEAEs related to study treatment,

- Adverse events of special interest (AESI) / AESI related to study treatment,
- Dose Limiting Toxicity / Dose Limiting Toxicity related to study treatment,
- TEAEs leading to death / TEAEs related to study treatment leading to death,
- TEAEs with NCI-CTCAE grade ≥ 3 / TEAEs related to study treatment with NCI-CTCAE grade ≥ 3 ,
- TEAE meeting any stopping rule,
- TEAE Related to Radiocopper Administration,
- TEAE related to Other Study Procedure.

In addition, the following tables will be produced by SOC and PT:

- TEAEs / TEAEs related to study treatment,
- Serious TEAEs / Serious TEAEs related to study treatment,
- Liver TEAEs / Liver TEAEs related to study treatment,
- TEAEs and maximum CTCAE grade / TEAEs related to study treatment and maximum CTCAE grade,
- TEAEs leading to death / TEAEs related to study treatment leading to death,
- Non-serious TEAE.

A patient with multiple occurrences of an AE will be counted only once in the AE category. SOCs will be sorted by descending order of frequency for the overall group, PTs will be sorted by descending order of frequency for the overall group within each SOC.

All deaths and on-treatment deaths will be listed together with the corresponding reasons.

The following listings will be provided:

- All AEs, identifying events collected during the pre-treatment and on-treatment,
- Serious AE,
- Non-Serious AE.

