9.2 Adverse Events

9.2.1 Definition of Adverse Events

An AE is defined as any untoward medical occurrence in the form of signs, symptoms, abnormal laboratory findings, or disease that emerges or worsens during an interventional clinical study with an IMP or NIMP, regardless of causal relationship and even if no IMP or NIMP has been administered.

Worsening of a pre-existing medical condition, (e.g., migraine headaches, gout) is to be considered an AE if there is either an increase in severity, frequency, or duration of the condition or an association with significantly worse outcomes.

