9.2.6 Recording Adverse Events

As quality and precision of acquired AE data is of key importance, the Investigator should use the AE definitions provided in above sections and observe the following guidelines when completing the AE pages of the eCRF:

- Whenever possible, recognized medical terms should be used to describe AEs rather than colloquialisms (for example, 'influenza' rather than 'flu'), and abbreviations should be avoided.
- AEs should be described using a specific clinical diagnosis rather than component signs or symptoms, if this is available (for example, 'congestive heart failure' rather than 'dyspnea, rales and cyanosis'). However, signs and symptoms considered unrelated to an identified disease or syndrome should be reported as individual AEs in the eCRF.
- AEs occurring secondary to other events (e.g., sequelae or complications) should be identified by the primary cause. A primary AE, if clearly identifiable, generally represents the most accurate clinical term to record in the AE pages of the eCRF.

Additional guidance can be found in the eCRF completion conventions provided by the Sponsor.

An Adverse Event (AE) is any untoward medical occurrence in a study subject which is temporally associated with the use of a medicinal product or study conduct, regardless of its potential relationship to the medicinal product or study conduct. An AE, therefore, can be any unfavorable or unintended sign, including any abnormal laboratory finding, symptom, or disease (new or exacerbated), whether or not related to the IMP or study

Protocol VTX-801_CLN_001	Investigational Product: VTX-801
	Version: 9 dated 07 AUG 2023
	Author: Aixial Group CRO

conduct. AEs should be followed-up in accordance with the procedures described in Section 9.2.7.

AEs will be captured differently in the eCRF depending on the date of onset and causality assessment (per Investigator's judgment) as described below:

Table 16 Capture of Adverse Events in the eCRF

AE onset date	Types of AEs to be captured in the eCRF
From signing the ICF, including Screening 1 and until start of Screening 2	
 Only AEs considered to be possibly, probably or definitely related to the study procedures
From Screening 2 included until 1-year post VTX-801 infusion visit included	
 All AEs

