11.4.4.1 Adverse Events

AEs will be coded using the Medical Dictionary for Regulatory Activities (MedDRA). System Organ Class (SOC), High-Level Group Term (HLGT), High Level Term (HLT), Preferred Term (PT), and Lower-Level Term (LLT) will be attached to the clinical database.

AEs will be summarized based on the date of onset for the event. Summaries (number and percentage of patients) of treatment-emergent AEs will be provided by SOC and PT, by dose cohort and overall.

Treatment-emergent adverse event is defined as any AE that emerges during or after IMP administration having been absent pre-treatment or worsens relative to the pre-treatment state.

Events that are considered possibly, probably or definitely related to the IMP, deaths, SAEs, and AEs resulting in IMP discontinuation will also be tabulated by SOC and PT.

A tabulation will also be provided that summarizes at least treatment-emergent and treatment-related AEs (possibly, probably or definitely related) by maximum severity (i.e., CTCAE grade).

Duration of AEs will also be investigated as appropriate.

All AEs, including treatment-emergent and non-treatment-emergent AEs, will be listed in patient data listings.

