11.5 Changes to the Planned Statistical Methods

Changes to the planned statistical methods will be documented in the clinical study report(s).

Protocol VTX-801_CLN_001	Investigational Product: VTX-801
	Version: 9 dated 07 AUG 2023
	Author: Aixial Group CRO

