8.2 Planned Interim Analysis Details

An interim analysis was planned to occur 1 year after the last patient was treated with VTX-801, per protocol. Due to the treatment premature discontinuation, the IA will occur before the 1-year period is reached after the last patient is treated with the study drug. Also, the IA will mainly focus on safety data.

9 Changes from Study Protocol

Due to early termination of the treatment, below is the list of changes from protocol:

- When the decision has been made to early terminate the treatment phase of the study, only 4 patients were dosed from US sites (2 in cohort 1 and 2 in cohort 2),
- The interim analysis will cover the study up to the early termination visit, occurring prior the end of the 1 year period after last patient was treated,
- The final analysis will cover the safety follow-up period after the study was prematurely discontinued,
- Pharmacodynamics Set and Efficacy Set will not be used for any of the TFLs,
- Pharmacodynamics and efficacy analysis will be limited to descriptive statistics,
- SoC withdrawal related data will not be produced,
- Shift tables will not be produced for laboratory evaluations,
- MELD has been calculated with an outdated formula. Footnote will be added to MELD-related outputs for reader's information.

10 References

- [1] ICH guidelines - E9: Statistical Principles for Clinical Trials, Adopted in EU by CPMP, March 1998, issued as CPMP/ICH/363/96
- [2] ICH guidelines - E3: Structure and Content of Clinical Study Reports, Adopted in EU by CPMP, December 95, issued as CPMP/ICH/137/95

11 Appendices

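### The SAP's definition of treatment-emergent AEs differs from the protocol's in both directions, and the difference is not declared among the SAP's changes from protocol

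*SAP*

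**What the plan says.** Protocol 11.4.4.1 gives a TEAE two limbs. It is "any AE that emerges during or after IMP administration having been absent pre-treatment or worsens relative to the pre-treatment state". The same section says that AEs enter the summaries by their onset date.

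SAP 7.9.1 uses a single criterion: "AEs that occurred during on-treatment period, from the day of VTX-801 dosing". The SAP does not define the on-treatment period, has no AE definition of its own, and mentions worsening nowhere else.

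SAP Section 9 opens with "Due to early termination of the treatment, below is the list of changes from protocol" and has eight bullets. None concerns the TEAE definition.

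On recording, Protocol 9.2.1 says that worsening of a pre-existing condition "is to be considered an AE if there is either an increase in severity, frequency, or duration of the condition". Protocol 9.2.2 requires changes in an AE's severity to be documented. Protocol 9.2.6 adds "Additional guidance can be found in the eCRF completion conventions provided by the Sponsor". Those conventions are not part of the protocol or SAP.

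**The concern.** TEAEs are the first item named in the primary endpoint (Protocol 3.2.1, repeated in SAP 4.1), and the abbreviated study report is to focus on safety (SAP 8.1). TEAE tables are therefore central to what will be reported.

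The setting makes disagreement between the two definitions possible. Protocol Table 16 captures all AEs from Screening 2, and sirolimus starts at Visit 2 (Day -7), so an AE can begin before dosing. Visit 6 includes procedures before the infusion and IV methylprednisolone one hour before it, so an AE can also begin on dosing day but before VTX-801.

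If the tables follow the SAP rule while readers assume the protocol's, the reported counts may not mean what the protocol says they mean. SAP Section 9 would not alert them. Section 9 also drops the laboratory shift tables, which removes another tabular view of worsening from baseline.

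**Working it through.** The plan gives no figure to reproduce, so the check sets the two definitions side by side and then works out the scale.

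**Step 1: which events are classified differently?**

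| Event | Protocol 11.4.4.1 | SAP 7.9.1 |
|---|---|---|
| New AE during or after infusion | TEAE | TEAE |
| Pre-dose AE worsens after infusion, entered as a new record with post-dose onset | TEAE | TEAE |
| (a) Pre-dose AE worsens after infusion, kept on its existing record | TEAE by the second limb | Could be left out |
| (b) AE starts on dosing day before the infusion | Not a TEAE | TEAE |
| (c) AE present pre-treatment, resolves, recurs post-dose without worsening | Arguably not a TEAE | TEAE |

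In case (a) the SAP is narrower. In (b), and arguably in (c), it is broader. The net effect on counts has no fixed sign.

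**Step 2: is the window for pre-dose onset real?** Screening 2 is nominally Day -49 to Day -14. All AEs are therefore captured for about 14 to 49 days, or 2 to 7 weeks, before dosing.

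**Step 3: how much output carries the label?** Counted from the lists in SAP 7.9.1:

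- Overview table: 10 lines. Eight are labelled TEAE (all, serious, liver, death, Grade 3 or higher, stopping rule, radiocopper, other procedure). Two are not (AESI, dose-limiting toxicity).
- Seven overview lines are paired with a treatment-related count and three are single: 7 × 2 + 3 = 17 counts. Of these, 5 × 2 + 3 = 13 are labelled TEAE.
- Tables by SOC and PT: 6 lines, five paired and one single: 5 × 2 + 1 = 11 tables, all labelled TEAE.

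These figures show how widely the definition is used. They do not show how many entries would be wrong.

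**Step 4: what can one patient change?** SAP Section 9 gives 2 patients dosed in cohort 1 and 2 in cohort 2. Each patient is counted once per category, and percentages use the number of patients in the set (SAP 7.1).

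- Patient already counted on the line: change 0.
- No other qualifying event on the line: 1/2 = 50 percentage points in the cohort and 1/4 = 25 overall. The line falls in case (a) and rises in (b) or (c), relative to the protocol's definition.

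**Step 5: is the change declared?** Section 9 does not mention it. Its opening ties the list to early termination, yet it also includes "MELD has been calculated with an outdated formula", so the list was not kept strictly to that cause.

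**The case against.** Six points can be made for the SAP.

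1. Its verb is *occurred*, not *started*, and Protocol 9.2.1 defines an AE as something that emerges or worsens. A post-dose worsening can be read as occurring on treatment. That reading is available, but the SAP does not state it. It also does nothing for cases (b) and (c).
2. The protocol contributes to the gap in case (a). It summarizes by onset date and does not say how worsening on an existing record overrides that date. This stands: the handling is unsettled in both documents. The missing limb and the dosing-day start are still the SAP's own.
3. If the eCRF conventions open a new record on worsening, case (a) disappears. This also stands, and the documents do not show whether they do.
4. Protocol 11.5 places documentation of method changes in the study report, and Section 9 is framed around early termination. Silence in Section 9 is therefore not in itself a breach, and nothing suggests that the change was meant to be hidden. It does mean that a reader of the SAP cannot tell whether the narrower wording was intended.
5. Every AE is listed with its pre-treatment or on-treatment status. Some worsened events also reach the overview's AESI line, because Protocol 9.6 includes ALT at 1.5 times baseline or more, suspected drug-induced liver injury, and neurological, psychiatric or behavioral AEs that worsen from baseline. This limits the harm to the tables. However, no stated flag marks post-dose worsening in the listing.
6. The trial is descriptive, with four patients and no hypothesis tests, so no inference depends on the counts. This is correct, and it keeps the point below a major defect.

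**Conclusion.** The mismatch is real and is fixed by the text. The SAP's TEAE rule is not the protocol's, it departs in both directions, and Section 9 does not say so. It should be corrected because TEAEs belong to the primary endpoint and the correction is cheap.

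The size is conditional. One affected patient moves a line by 0, or by 50 points in a cohort and 25 overall, up or down. Case (a) assumes that worsening stays on the existing record and that *occurred* is applied as onset date. Case (b) assumes an AE with onset on dosing day before infusion. Case (c) rests on reading *absent pre-treatment* as excluding an AE that had resolved before dosing.

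A reader might infer that the SAP systematically undercounts TEAEs. The documents do not support that, since (b) and (c) push counts up. Nor do they show that any reported table is wrong or that any AE is lost from the report: no such event is shown to have occurred, and all AEs are listed.

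**What to change.** - Restore the protocol's two-limb definition in SAP 7.9.1.
- State that a pre-dose AE whose recorded grade after dosing exceeds its last pre-dose grade counts as a TEAE, whether it stays on the same record or is opened as a new one. If dated grade changes are not in the database, flag such events in the all-AE listing instead.
- Classify dosing-day AEs by onset time relative to the infusion where a time is recorded, and otherwise as treatment-emergent. This default agrees with the worst-case date imputation in SAP 5.2.
- If the dosing-day rule is kept on purpose, declare it in Section 9 and flag worsened pre-dose AEs in the listing.
- If the eCRF conventions already open a new record on worsening, one sentence saying so settles case (a).

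The cost is a short text change and one extra derivation or listing flag for four patients. TEAE counts may rise or fall slightly.

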After the 1-year post infusion visit until completion of the 5-year follow-up visit included	
 All AEs except those AEs incontrovertibly unrelated to VTX-801, radiocopper and study procedures
After the 5-year follow up period	
 Only SAEs considered to be possibly, probably or definitely related to VTX-801

Abbreviations: AE= Adverse Event; eCRF= electronic Case Report Form; ICF= Informed Consent form; SAE= Serious Adverse Event.

Note: The above table refers to newly onset AEs. *Follow-up* details regarding the AEs previously entered into the eCRF will be captured regardless of the type of AE. (Refer to Section 9.2.7).

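### TEAE percentages by cohort take no account of follow-up time, although sequential dosing gives the lower-dose cohort longer follow-up at the interim cut

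*SAP*

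**What the plan says.** SAP 7.9.1 sets the main TEAE display: "An overview summary table will present the number and percentage of patients with a TEAE". The safety tables group patients by dose cohort: "All safety analyses will be performed using descriptive statistics by cohort and overall using the SAF, unless otherwise specified" (SAP 7.9). SAP 7.1 fixes the denominator: "All summary percentages will be calculated using N as the denominator, unless otherwise stated", where "N will be the number of patients in the specified population and cohort". Under SAP 7.9.1, "A patient with multiple occurrences of an AE will be counted only once in the AE category". TEAEs are "AEs that occurred during on-treatment period, from the day of VTX-801 dosing"; the definition gives a start but no end. SAP 7.7 lists infusion parameters only. I found no summary of follow-up duration, common observation window or time-to-event summary in the SAP.

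On timing, Protocol 4.2 doses consecutive cohorts in ascending order. It requires at least 6 weeks between the first two patients of a cohort, and review of at least 12 weeks of data from both before escalation. SAP 8.2 says "the IA will occur before the 1-year period is reached after the last patient is treated with the study drug", and SAP 9 runs the interim up to the early termination visit, with 2 patients dosed in each of cohorts 1 and 2.

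On AE capture, the table in Protocol 9.2.6 collects all AEs up to the 1-year visit. After that it collects "All AEs except those AEs incontrovertibly unrelated to VTX-801, radiocopper and study procedures".

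**The concern.** A percentage of patients ever having an event rises with time observed. When patients dosed in sequence are cut at about the same calendar date, those dosed first have been observed longer, and here they are the lower-dose patients. Two cohorts with the same underlying event rate would then be expected to show a higher percentage at the lower dose, and a real excess at the higher dose would look smaller than it is. The primary objective is the safety of ascending doses, so the distortion runs in the unhelpful direction.

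The overview table also has rows for TEAEs related to radiocopper and to other study procedures. Exposure to the Week 36 radiocopper injection and the Week 52 biopsy depends on how far each patient has got.

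**Working it through.** The plan gives no event rate or follow-up figure to reproduce, so the check derives follow-up from the dosing rules.

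**Inputs from the documents.** Two patients per cohort (SAP 9); at least 6 weeks between the first two patients and at least 12 weeks of data on both before escalation (Protocol 4.2); last patient followed for less than 52 weeks at the interim (SAP 8.2).

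**Assumptions.** Minimum spacing; one calendar cut for all; no early withdrawal; the TEAE window runs to the cut. The last patient's follow-up, T weeks, is not given and is varied. The event rate is assumed constant and equal in both cohorts.

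**Dosing weeks.** Cohort 1: 0 and 6. Cohort 2: 6 + 12 = 18, and 18 + 6 = 24.

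**Follow-up at the cut.** Cohort 1: T + 24 and T + 18, mean T + 21. Cohort 2: T + 6 and T, mean T + 3. The difference is 18 weeks for any T. The ratio is (T + 21)/(T + 3).

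**Expected crude percentage.** The mean over the cohort's two patients of 1 − exp(−rate × weeks/52). For T = 30 and 0.5 per patient-year:
- cohort 1 (54 and 48 weeks): 40.5% and 37.0%, mean 38.7%;
- cohort 2 (36 and 30 weeks): 29.3% and 25.1%, mean 27.2%.

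| T (weeks) | Patient-weeks, cohort 1 v 2 | Ratio | 0.25/year | 0.5/year | 1/year |
|---|---|---|---|---|---|
| 12 | 66 v 30 | 2.20 | 14.7% v 6.9% | 27.2% v 13.4% | 46.9% v 24.9% |
| 30 | 102 v 66 | 1.55 | 21.7% v 14.7% | 38.7% v 27.2% | 62.4% v 46.9% |
| 39 | 120 v 84 | 1.43 | 25.1% v 18.3% | 43.8% v 33.2% | 68.4% v 55.3% |
| 51 | 144 v 108 | 1.33 | 29.3% v 22.9% | 49.9% v 40.5% | 74.9% v 64.5% |

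**Time after Year 1.** Weeks beyond 52 at T = 51: cohort 1, (75 − 52) + (69 − 52) = 40 of 144 patient-weeks; cohort 2, 57 − 52 = 5 of 108. At T = 30 it is 2 of 102 v 0 of 66.

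**Common window.** Cutting every patient at T weeks after dosing gives 2T patient-weeks in each cohort. Because T < 52, the window stays within the period when all AEs are captured.

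**Check on a patient-year rate.** Suppose each cohort has one early event and T = 30. The rates are 1/(102/52) = 0.51 and 1/(66/52) = 0.79 per patient-year. Cohort 2 looks 1.55 times worse although the event experience is identical.

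**The case against.** The best counter-argument is that four patients cannot show a dose relationship under any adjustment. Each cohort percentage can only be 0, 50 or 100, and the exact 95% interval for 1 of 2 is 1.3% to 98.7%. Protocol 11.4 rules out hypothesis testing. SAP 7.9.1 lists every AE, and SAP 7.9.2 and 7.9.4 summarise laboratory and ECG values by visit, so those are compared at like times. The table and listing shells are in a separate document and may already show onset day or follow-up. All of this stands, and it limits the weight of the point. It does not explain why the SAP specifies cohort percentages without follow-up beside them.

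The constant rate is also open to challenge. After a single infusion, the protocol expects infusion reactions within 24 hours (2.5) and most ALT rises within 12 weeks (4.4). For events like these, extra late follow-up changes the percentages little. This stands too.

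Four stronger readings are tempting, but the documents do not support them.
- The visit table in SAP 5.1 runs to Month 24, so a reader might infer something like 24 v 9 months, giving 63% v 31% at 0.5 per year (1 − exp(−1.0) and 1 − exp(−0.375)). That table only lists visit labels; it does not show that any cohort 1 patient reached Month 24.
- A reader might see the narrower capture after Year 1 as a second bias in the same direction. Only incontrovertibly unrelated AEs are dropped, so related TEAEs should be unaffected. For all-cause TEAEs the change lowers cohort 1's count and partly offsets its longer follow-up.
- A reader might extend the imbalance to the final analysis. The protocol planned 5 years for everyone, and SAP 3 now says the follow-up is reduced without giving its length, so balance at that point is unknown.
- A reader might propose events per patient-year as the remedy. A single rate mixes two capture rules and, as calculated, can penalise the shorter-followed cohort.

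**Conclusion.** The point holds for the interim analysis. Crude TEAE percentages by cohort compare unequal follow-up in a direction that can flatter the higher dose. The 18-week mean difference follows from the minimum spacing, a common calendar cut and no early withdrawal. Wider actual spacing would increase it. Protocol 6.5 allows 4 weeks for an early termination visit, so differing visit dates could move the mean difference by up to 4 weeks either way (14 to 22). At 0.5 events per patient-year, the expected gap is about 9 to 12 percentage points for last-patient follow-up of 51 down to 30 weeks, and less if events fall early. The rate and T are assumptions; the documents give neither. With 2 patients per cohort this is a presentational weakness worth correcting cheaply. It does not invalidate the safety reporting.

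**What to change.** In SAP 7.9.1:
- report follow-up duration for each patient and by cohort beside the TEAE tables;
- add one TEAE overview table for a common window, from dosing to the shortest follow-up of any patient;
- keep the all-time tables, so that late events stay visible;
- do not present a single events-per-patient-year rate across the 1-year change in AE capture.

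The cost is one repeated table and a few rows, with no new data. The downside is that events after the window appear only in the all-time tables.
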